5.4 Handling of Partial or Missing Times within Study Day

For imputation of the missing primary and secondary endpoints TOTPAR4, 6 and 8, please refer to Section 8.3 as below. Any assessments with partial or missing times will be considered unreliable and removed from the analyses. For assessments with partial times (hours present and minutes missing, or vice versa), the following process will be followed:

- For time points less than 1 hour from start of drug administration for the 24-hour clock
 - : intended format in the CRF,
 - If hour is missing, the minutes will be used to calculate the time from the start of drug administration.
 - If both hour and minutes are missing, the value will remain missing.
- For time points greater than 1 hour from start of the study medication,
 - If the minutes are missing, the missing minutes will be imputed to the same minutes as in the prior sampling time.
 - If the minutes from all prior time points are missing, the missing minutes will be imputed to the minutes of the subsequent time points.
 - If all time points have minutes missing, then they will all be set to 0 minutes.
 - If hour is missing, the value will remain missing.

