10.5 Rescue medication

Details on rescue medication are provided in Section 1.4.2.

Subjects can request and take rescue medication at any time after the first administration of the IMPs if their trial medication does not provide sufficient pain relief. However, they will be encouraged (but not required) to refrain from rescue medication intake until at least 120 minutes after the intake of the first dose of IMPs (i.e., until diclofenac and tramadol have reached their maximum plasma concentration) to be able to reliably assess the efficacy of the IMPs first.

The time will be registered when subjects first request rescue medication and the time they take their first dose. Subjects taking rescue medication will be asked to complete the trial procedures as planned.

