8.3 Handling of Dropouts or Missing Data

Diligent attempts will be made to limit the amount of missing data in the pain relief assessments used to determine the primary efficacy endpoint. Efforts will be made to encourage but not to enforce subjects to not start rescue medication intake if not needed. Assessments with missing date/time of evaluation will be considered unreliable and removed from all analyses and treated as missing values. Assessments made after the subject's first dose of rescue medication will be considered missing values and excluded from the analyses. Other than the methods outlined below for TOTPAR4, TOTPAR6, and TOTPAR8, no imputations will be performed to replace missing values for any of the other endpoints; those missing values will be left as missing.

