Appendix A: Definitions for Efficacy Endpoints

1. Pain Intensity and Numerical Rating Scale (NRS)

11-point Numerical Rating Scale (NRS) is used to evaluate pain intensity.

Pain Intensity Rating Scale

Please rate your pain by selecting the one number that best describes how much pain you have right now:

Pain intensity: Subjects will be asked to assess their current pain by selecting a number corresponding to their pain, with anchors at 0 for “no pain” and 10 for “pain as bad as you can imagine”. The subjects will be asked to answer the following question:

“Please rate your pain by selecting the one number that best describes how much pain you have right now”.

Pain intensity will be categorized as:

- None NRS score of 0
- Mild NRS score of ≥ 1 and < 5
- Moderate NRS score of ≥ 5 and ≤ 6
- Severe NRS score of ≥ 7

NRS pain scores will be assessed before the first dose of IMPs, and 15, 30, 45, 60, and 90 minutes (± 2 minutes), and 2, 3, 4, 5, 6, 7, 8, 16, and 24 hours (± 6 minutes) after the first dose of IMPs.

2. Pain Relief and Verbal Rating Scale (VRS)

The subject's pain relief will be assessed using a 5-point Verbal Rating Scale (VRS) by completion of the following statement.

"My relief from starting pain is"

- None (0)
- A little (1)
- Some (2)
- A lot (3)
- Complete (4)

Pain relief will be assessed 15, 30, 45, 60, and 90 minutes (± 2 minutes), and 2, 3, 4, 5, 6, 7, 8, and 16 hours (± 6 minutes) after administration of the first dose of IMPs.

3. Total Pain Relief at 4, 6, and 8 hours (TOTPAR4, TOTPAR6, and TOTPAR8)

Total Pain Relief (TOTPAR) will be defined as $\sum PR_t \times$ [time (hours) elapsed since previous observation] where PR_t is the Pain Relief at time point t in comparison to the assessment before administration of IMPs. The TOTPAR will be calculated at 4, 6, and 8 hours.

4. Peak Pain Relief

Peak pain relief will be defined as the maximum pain relief score for the subject over the 16 hours after administration of the first dose of IMPs, but prior to the intake of any rescue medications.

5. Pain Intensity Difference (PID)

Pain Intensity Difference (PID_t) will be defined as the difference between baseline pain intensity and pain intensity at time point t (e.g., baseline score - time point t score). The PID (11-point NRS) compared to baseline at 15, 30, 45, 60, and 90 minutes, and at 2, 3, 4, 5, 6, 7, 8, and 24 hours will be calculated.

6. Summed Pain Intensity Difference (SPID)

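### SAP 5.4 both removes and fills partial assessment times, and if filling is used the copied-minutes rule misplaces the 90-minute and 2-hour ratings by about 30 minutes

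*SAP*

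**What the plan says.** SAP 5.4 contains three instructions that do not fit together.

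- A pointer: "For imputation of the missing primary and secondary endpoints TOTPAR4, 6 and 8, please refer to Section 8.3 as below".
- A removal rule: "Any assessments with partial or missing times will be considered unreliable and removed from the analyses".
- A filling process, in the very next sentence: "For assessments with partial times (hours present and minutes missing, or vice versa), the following process will be followed".

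The filling process has two branches, for time points under 1 hour and over 1 hour. The second opens "For time points greater than 1 hour from start of the study medication" and instructs: "If the minutes are missing, the missing minutes will be imputed to the same minutes as in the prior sampling time". If all prior minutes are missing, the minutes of later time points are used; if every time point lacks minutes, zero is used.

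SAP 8.3 drops assessments whose date or time of evaluation is missing and treats them as missing values. It does not mention partial times.

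The rating schedule is in SAP Appendix A, item 2: "Pain relief will be assessed 15, 30, 45, 60, and 90 minutes (± 2 minutes), and 2, 3, 4", then hourly to 8 hours and once more at 16 hours, with a ±6 minute window from 2 hours on.

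On rescue, SAP 8.3 says that assessments made after a subject's "first dose of rescue medication will be considered missing values and excluded from the analyses". For TOTPAR, SAP 8.3.1 then substitutes 0 in the combination arms and 0.375 in the monotherapy arms. Protocol 10.5 says subjects are "encouraged (but not required) to refrain from rescue medication intake until at least 120 minutes after the intake of the first dose of IMPs".

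**The concern.** There are two linked problems. First, a programmer cannot tell from SAP 5.4 whether a rating with a recorded hour but no minutes is dropped or completed. Second, if it is completed, the formula does not suit the schedule. Copying the previous minutes assumes that consecutive ratings are whole hours apart, and two ratings within the rule's scope and within the 4-hour primary window are not.

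The 2-hour rating is the sensitive one, because the advice to wait 120 minutes makes first rescue close to that rating plausible. If a filled clock time is compared with the rescue time, a 30-minute error can put the score on the wrong side of rescue. Timed endpoints such as time to pain half gone would take the error directly if their event times come from the filled clock time.

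**Working it through.** **Inputs.** Rating times 15, 30, 45, 60 and 90 minutes and 2, 3 and 4 hours; windows ±2 minutes up to 90 minutes and ±6 minutes from 2 hours (SAP Appendix A). Fill rule (SAP 5.4). Substitution values 0 and 0.375 (SAP 8.3.1). TOTPAR as the sum of score times hours since the previous rating (SAP 8.1.1).

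**The plan's own figure.** The nominal weights to 4 hours are 0.25 × 4 + 0.5 × 2 + 1 × 2 = 4 h. With a top score of 4, the maximum TOTPAR4 is 4 × 4 = 16, as SAP 8.1.1 states. The documents give no figure for the error of the minutes rule.

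**What the fill does.** Let p be the prior rating's clock time and a the actual time of the rating with missing minutes. The filled time is the recorded hour of a plus the minutes of p. For these steps it equals p if no hour mark lies between the two ratings, and p + 60 minutes if one does.

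**Half-hour steps.** Write a − p = 30 + d, where d is the net deviation from schedule. The error (filled minus actual) is −(30 + d) without an hour mark between the ratings and 30 − d with one. At nominal times d = 0:

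| Dose minute | 90-minute rating placed at | 2-hour rating placed at |
|---|---|---|
| 00-29 | 60 min (30 early) | 150 min (30 late) |
| 30-59 | 120 min (30 late) | 90 min (30 early) |

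Example: dose 10:10, 90-minute rating at 11:40, 2-hour rating at 12:10. With minutes missing, the 90-minute rating becomes 11:10, the same time as the 60-minute rating. With its minutes missing instead, the 2-hour rating becomes 12:40.

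Enumerating all 60 dose minutes gives 30 early and 30 late at each rating, and none correct. With windows, d runs from −4 to 4 at 90 minutes and from −8 to 8 at 2 hours, so the absolute error is 26-34 and 22-38 minutes. Every filled time lies outside its window. About half fall on the previous rating's own time.

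One exception: if the 90-minute minutes are also missing and are filled first from the 60-minute rating, the 2-hour rating inherits the 60-minute minutes and its nominal error is 0.

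**Whole-hour steps.** At nominal times the error is 0 at 3 hours and at each hourly rating to 8 hours. Within the windows the minutes can straddle an hour mark. Example: 2-hour rating 11:58, 3-hour rating truly 13:01, filled as 13:58, which is 57 minutes late. For a net deviation of |d| minutes the chance of straddling is |d|/60. With both ratings spread evenly over −6 to +6 whole minutes, the mean |d| is (13² − 1)/(3 × 13) = 4.31, so the rate is 4.31/60 = 7.2%, or about 7%. The error is then 60 − |d|, between 48 and 59 minutes.

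**If filled times decide rescue status.**

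- A 2-hour rating moved to 150 minutes is wrongly discarded when rescue falls between 2 h and 2 h 30.
- A 2-hour rating moved to 90 minutes is wrongly kept when rescue falls between 1 h 30 and 2 h.

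At the nominal 0.5 h weight, swapping a score s for the substitute δ changes TOTPAR4 by 0.5 × (s − δ). For s = 4 this is 2.0 points (δ = 0) or 1.81 (δ = 0.375); for s = 2 it is 1.0 or 0.81.

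**If recorded times are also used as weights.** Filling the 90-minute rating changes its weight from 0.5 h to 0 or 1.0 h, and the 2-hour weight becomes 1.0 or 0 h. The total is unchanged. The net effect is 0.5 × (difference between the two scores), or 0.5 point for a one-category difference.

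**Scale on an arm mean.** The count of affected subjects is not in the documents. As an assumption, with 180 evaluable subjects per arm and the largest change of 2.0 points each, one affected subject moves the arm mean by 2.0/180 = 0.011, and nine (5%) move it by 18/180 = 0.10.

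**The case against.** The strongest objection is that the harm may never arise. SAP 5.4 sends TOTPAR to 8.3 and says outright that partial times are removed. Under removal no filled time exists, no score changes sides of rescue, and an intermittent gap in TOTPAR is carried forward under 8.3.1. That stands, and it makes the rescue consequence conditional. It does not remove the point: the next sentence of 5.4 prescribes filling, and 8.3 speaks of missing rather than partial times, so a time completed under 5.4 could be read as no longer missing. If the contradiction were resolved in favor of filling, the formula would still be wrong.

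Other parts of the objection also stand. The documents do not say that rescue status is decided from a filled clock time, and they give no distribution of rescue times. The affected ratings are made on site (Protocol 11.1.2.1), and the electronic CRF raises automatic queries for missing data (Protocol 13.3), so partial times should be few. Whether TOTPAR uses actual or nominal elapsed times is open; the stated maximum of exactly 16 fits nominal weights better.

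A reader might infer that the rule is always wrong by exactly 30 minutes. It is not: the exact figure holds only at nominal times with the prior minutes recorded, and the sequential-fill case gives 0 at 2 hours. A reader might also infer that a 90-minute weight of 0 or 1.0 h distorts TOTPAR4 by that full amount. It does not, because the 2-hour weight offsets it.

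**Conclusion.** The point holds in conditional form. SAP 5.4 contradicts itself on partial times. If its filling process is applied, the copied-minutes rule gives a wrong time at the two half-hour steps whenever the prior minutes are recorded, and an error of nearly an hour in about 7% of fills at 3 and 4 hours. The 7% assumes rating times spread evenly over the windows.

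The consequence for an affected subject is at most 2.0 TOTPAR4 points through rescue misclassification, provided that filling overrides removal and that filled times set rescue status. A reader might set those 2.0 points against the non-inferiority margin of 1.5 and conclude that the primary result is at risk. The documents do not support that: the margin applies to a difference in arm means, and the number of partial times is not given and is probably small. This is a minor correction, worth making because the stated rule is wrong where it applies and is easily replaced.

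**What to change.** State one rule for partial times in SAP 5.4 and use the same wording in 8.3.

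- **Removal:** keep the removal sentence, delete the filling bullets, and have 8.3 name partial as well as missing times.
- **Filling:** delete the removal of partial times from 5.4 and say in 8.3 that a completed partial time does not count as missing. Replace the minute-imputation bullets with *first-dose time plus the nominal time point* for all ratings from 1 hour on. Include exactly 1 hour, which the current branches (under and over 1 hour) leave out.

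With nominal times, a rating made within its window is off by at most 2 or 6 minutes, so only rescue taken within that span of the rating could still be misordered.

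The cost is SAP wording and one line of derivation code. SAP Section 1 already provides for documenting such a change in an amendment before database lock.

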5.5 Visit Windows

The frequency of the assessments was based on the literature available for previous trials with other kinds of drugs using the dental pain model (third molar extraction). The trial course will comprise 4 visits: 3 visits for which subjects have to be at the trial site, and 1 visit which can be a phone call or an on-site visit. At any time during the trial, the investigator may ask the subject to come for an unscheduled additional visit outside the trial schedule if deemed necessary according to his/her normal practice. Screening period is expected to happen before the informed consent form is signed.

5.6 Review of Blinded Data

A number of analyses may require review of blinded data prior to database lock. The following reviews may occur while the study is ongoing or prior to database lock. Subject ID will be masked in all of these reviews to avoid introducing any bias.

- Concomitant medications are reviewed independent of Subject ID to identify prohibited medications
- Review of adverse event summaries and listings to identify MedDRA preferred terms chosen are consistent with drug's mechanism of action.
- Review of protocol and consent deviations to identify major deviations that would exclude subjects from the per-protocol population.
- Review of subjects with a missing or partial last dose date on the Study Exit Status CRF in order to determine an appropriate imputed date or other missing or partial dates for a parameter of interest; if deemed necessary.
- Reasons for withdrawal which are potentially treatment related

6. ANALYSIS POPULATIONS

The following subject populations will be used for various safety and efficacy analyses:

- The Enrolled Set will comprise all subjects who signed the informed consent form.
- The Safety Set will comprise all subjects allocated and treated with IMPs. Analyses on the Safety Set will be conducted according to actual treatment received.
- The Full Analysis Set (FAS) will comprise all subjects allocated and treated, and with at least 1 non-missing pain relief assessment during the first 4 hours post-baseline. Analyses on the FAS will be conducted according to allocated treatment.
- The Per Protocol Set (PPS) will comprise a subset of the subjects in the FAS without any major protocol deviations (see Section 7.2) affecting the primary endpoint analysis. Only subjects with no rescue medication use in the first 120 minutes after first dose, who complete at least a follow-up of 4 hours and who comply with the protocol procedures will be included in the PPS. Analyses on the PPS will be conducted according to actual treatment received.

7. STUDY POPULATION

7.1 Subject Disposition

Subject disposition information will be summarized for all subjects by treatment group, overall and by site. Summaries will include: the number of randomized subjects, the number of subjects in each analysis population, the number of subjects completing the study (and subsets completing the study on and off treatment), the primary reason for discontinuation of study drug, and the primary reason for discontinuation of study. The visit schedules and their timing are given in Section 1.8 of the protocol.

A listing of all early discontinuations from study drug, as well as discontinuation from the study will be provided.

7.2 Protocol Deviations

In accordance with International Conference on Harmonisation (ICH) E3, Sponsor-defined eligibility violations and post-randomization protocol deviations will be identified and listed

separately by study site and subject. Sources for these deviations may include IXRS, Trial Management or the clinical database. Deviations will be reviewed and classified as follows before database lock:

Deviation type/code as provided by Sponsor may include but is not limited to the following:

- Informed consent
- Randomization error
- Safety
- Efficacy
- IMP / Treatment deviation
- Other protocol deviations

Deviations are then categorized into:

- Major (Any deviation that impacts the safety or efficacy outcome of the study)
- Minor (Any non-major deviation)

A listing and tabulation of protocol deviations will be provided.

7.3 Demographic and Baseline Characteristics

Demographic variables to be summarized include the following: date of signing the informed consent, age at informed consent (in years), gender, ethnicity, race, smoking status, height (in cm), weight (in kg), and body mass index (BMI). The BMI will be calculated.

Baseline characteristics, which includes information from the dental surgical procedure, will be summarized for the following: number of molars extracted, impacted molars classification, impacted molar position, planned surgical procedure, duration of surgery (minutes), amount of Lidocaine used during of surgery (mg), time from end of surgery to first dose of study medications (hours), and baseline pain intensity (both on the numeric 11-point rating scale and as categorized as none/mild/moderate/severe).

Demographic and baseline characteristics will be summarized for all the analysis populations (FAS, PPS and Safety Set).

The frequencies and percentages of subjects in the following categories of smoking status will be summarized: current smokers (every day or on some days per week), recent former smokers (smoked within the last 12 months), long-term former smokers (smoked 1 to more than 15 years ago), and never smoked regularly. The number of cigarettes/cigars/pipes smoked per week will be displayed in the listing for current smokers.

7.4 Medical History

Verbatim terms on case report forms will be mapped to preferred terms and system organ classes using the Medical Dictionary for Regulatory Activities (MedDRA) (version 19.0).

Subjects' medical and surgical history, including any relevant diseases and surgical interventions, will be recorded at Visit 1. The number and percentage of subjects with a given medical and/or surgical history will be summarized for each system organ class. Summaries will be provided for the FAS, PPS and Safety Set. The verbatim and coded medical histories will be included in a listing.

7.5 Dental History

Subject's dental history will be presented in by-subject listings. The listings will include tooth extractions (within the last 6 months), any other dental surgeries (e.g., root canal), dental or periodontal disease, use of dentures, and other significant dental history.

7.6 Physical Examinations

A directed physical examination will be carried out at Visit 1 (Enrollment Visit). A complete Physical Examination (PE) should include assessments of the general condition, ears, nose and throat, mouth (including teeth and gums), head, neck, heart, and lung. Physical examination results must be available at the latest at Visit 2.

Prior to allocation to treatment, any clinically relevant findings from the physical examination will be documented as part of the medical history.

Physical examination results will be presented in by-subject listings. Summaries will be presented for the Safety Set and will include the number and percentage of subjects within each category by visit and by body system/parameter evaluated. For the physical examination, each body system is assessed as Clinically Significant or Not Clinically Significant.

7.7 Beta-human Chorionic Gonadotropin Pregnancy Test

Urine samples will be collected from women with a childbearing potential at Visit 1 and Visit 2. A urine β -human chorionic gonadotropin pregnancy dipstick test will be performed at the site. The results of the dipstick test will be listed.

7.8 Radiological Examinations

Radiological examinations of the affected third molars will be conducted at Visit 1 (Enrollment Visit), if this information is not available from a previous X-ray taken up to 1 month before the Enrollment Visit. These data will be presented in a by-subject listing.

7.9 Adverse Events

Adverse events will be documented from the time of enrollment (i.e., Visit 1, the time the informed consent form is signed) up to the time of the last protocol scheduled contact, i.e., date of last visit/contact (can be a phone call, e.g., in case of withdrawal). All adverse events reported spontaneously by subjects at any time point will also be documented. Adverse events occurring in the Enrollment Period but before first administration of an IMP and worsening on or after IMP administration will be documented as new adverse events.

The following information regarding all adverse events will be documented: description (adverse event reported term), start date/time, end date/time or continuation, whether adverse event was serious, intensity, outcome, action taken with IMPs, countermeasures, causal relationship to IMPs. The clinical intensity of an adverse event will be classified as: mild, moderate and severe. For adverse events where the intensity changes over time, the maximum intensity observed during the whole duration of the adverse event will be documented.

7.10 Laboratory Values

Clinical laboratory parameters (hematology, chemistry, coagulation and urinalysis) at Visit 1, Urine pregnancy at Visit 1 and Visit 2, will be collected, listed by subject and visit, and tabulated by visit for each parameter. Clinical laboratory parameter and urinalysis data must be available at the latest at Visit 2.

